The clinically significant adverse reactions discussed above are being monitored and have been identified as potential risks in the vernakalant IV Risk Management Plan (RMP). In addition, specific contraindications such as heart failure (NYHA III and IV), severe aortic stenosis, myocardial infarction (MI) or acute coronary syndrome (ACS) in 30 days prior to administration, prolonged QT at baseline (uncorrected  $>$  440 msec), severe bradycardia, sinus node dysfunction, second degree and third degree heart block in the absence of a pacemaker, and use of intravenous rhythm control antiarrhythmics (class I and class III) within 4 hours prior to vernakalant IV administration are also being monitored.

Key prescribing information from the SmPC are included as part of the package leaflet in the Brinavess™ packaging, and distributed with the product directly to the point-of care site. Additionally, the SmPC accompanies the HCP education card packs that are distributed to all anticipated prescribers and users of the product. In addition to this, SmPCs are handed out at the occasion of each customer contact, at national and international conferences, as well as in local educational events. The SmPC is accessible on Cardiome's Brinavess™ website through hyperlinks to the EMA website. The SmPC is

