## **9 EFFECTIVENESS**

### **9.1 Definition of Effectiveness Endpoint**

Effectiveness of vernakalant IV will be assessed as a secondary endpoint, defined as the proportion of patients who are converted to sinus rhythm for at least one minute within 90 minutes of start of first vernakalant IV administration. [Ref. 5.4: 104]

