**Exclusion Criteria**

The exclusion criteria for enrolment are:

1. Patients with the following contraindications:
  - Hypersensitivity to the active substance or to any of the excipients.
  - Patients with severe aortic stenosis, patients with systolic blood pressure  $< 100$  mm Hg, and patients with heart failure class NYHA III and NYHA IV.
  - Patients with prolonged QT at baseline (uncorrected  $> 440$  msec), or severe bradycardia, sinus node dysfunction or second degree and third degree heart block in the absence of a pacemaker.
  - Use of intravenous rhythm control antiarrhythmics (class I and class III) within 4 hours prior to, as well as in the first 4 hours after, BRINAVESS™ administration.
  - Acute coronary syndrome (including myocardial infarction) within the last 30 days.
2. Enrolment in an investigational drug or device clinical trial in the 30 days prior to study enrolment. Participation in another non-interventional drug or device study or registry is permitted.

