4.2 Analysis Populations

All screened patients will be included in summary of patient disposition with additional summary of their demographic characteristics. All enrolled patients who meet the eligibility criteria, sign the informed consent form, and are administered vernakalant IV will be included in the analysis population set, regardless of their disposition status. If a patient's consent is withdrawn prior to completing follow-up period, all data already collected as part of the study will be retained for analysis unless country-specific ethics committee (EC) requirements prohibit this or the patient requests otherwise. In addition, patients who discontinue from the study prior to receiving vernakalant administration will not be included in the overall analysis population. All the summaries will be presented on the overall analysis population set unless otherwise stated.

Patients may be enrolled in the study more than once in association with multiple administrations of vernakalant IV. Patients with multiple enrolments are included in the analysis population, and the number of previous study enrolments is provided in the study analysis. All study analyses presented in the study tables, listings, and figures of this report treat each patient's subsequent administrations of vernakalant IV as occurring independently.

Effectiveness analysis population is defined as all patients from overall analysis population defined above EXCEPT those who receive ECV or IV Class I/III AA for cardioversion within 90 minutes of start of the first vernakalant IV administration. But for analysis of the effectiveness of

vernkalant IV, e.g., rate of conversion, both analysis population and effectiveness population may be used.

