- Patients with at least one of the following contraindications: baseline systolic blood pressure < 100 mmHg, MI/ACS past 30 days, severe aortic stenosis, severe bradycardia in absence of pacemaker, prolonged QT at baseline (uncorrected > 440 msec) in absence of pacemaker, sinus node dysfunction in absence of pacemaker, 2nd or 3rd degree heart

block in absence of pacemaker, heart failure NYHA functional class III or IV, use of class I or class III intravenous anti-arrhythmics within 4 hours before, or within 4 hours after, the start of first vernakalant infusion).

In addition, the effectiveness of vernakalant will be evaluated by the indication of use for which vernakalant IV was prescribed (i.e., conversion of atrial fibrillation for non-surgery patient and conversion of atrial fibrillation for post-cardiac surgery patients).

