5.10 Secondary Objective #4: Rate of Conversion to Sinus Rhythm

For patients in the analysis population set and the effectiveness analysis population set, the rate of successful conversion to sinus rhythm for at least one minute within 90 minutes from the start of first vernakalant IV administration (Secondary Objective 4) will be expressed as the proportion of patients with successful conversion, together with the associated 95% confidence interval. (**Table 15a**). The rate of successful conversion to sinus rhythm without time restriction will also be expressed as the proportion of patients with successful conversion, together with the associated 95% confidence interval. The time (in minutes) from start of vernakalant infusion to conversion to sinus rhythm among those patients who converted will be summarised using appropriate measures of dispersion and central tendency (means, medians, ranges, Q1-Q3 ranges, and standard deviations) (**Figure 3**). As defined in Section 4.3, a pre-specified secondary analysis of the effectiveness of vernakalant will be restricted to a subgroup of patients who receive vernakalant IV in accordance with the SmPC (i.e., adult indication, therapeutic indication for AF, duration of AD \leq 7 days for non-surgery patients and \leq 3 days for post-cardiac surgery patients, and no contraindications) (**Table 15b**). Rates of successful conversion will also be

tabulated for all patients by non-surgery and post-cardiac surgery indications, respectively (**Table 15c, 15d**).

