¹ Includes patients who receive more than 1 infusion within a single treatment episode.

² Rate of conversion (%) is calculated as: (number of patients who have conversion to sinus rhythm for at least one minute with 90 minutes after first vernakalant infusion within effectiveness analysis population) / (total number of patients within effectiveness analysis population) x 100.

³ Rate of conversion (%) is calculated as: (number of patients who, within 90 minutes after first vernakalant infusion, have conversion to sinus rhythm for at least one minute but have no ECV or IV Class I/III AA within overall analysis population) / (total number of patients within overall analysis population).

⁴ Rate of conversion (%) is calculated as: (number of patients who, within 90 minutes after first vernakalant infusion, have conversion to sinus rhythm for at least one minute but have no ECV, oral propafenone/flecainide or IV Class I/III AA within overall analysis population) / (total number of patients within overall analysis population).

Template of Table 15a will be applied to the following three tables.

Table 15b Proportion of Patients Converted to Sinus Rhythm and Time to Conversion Following Vernakalant Infusion (SmPC Subgroup Analysis)

Table 15c Proportion of Patients Converted to Sinus Rhythm and Time to Conversion Following Vernakalant Infusion (Non-Surgery Patients)

Table 15d Proportion of Patients Converted to Sinus Rhythm and Time to Conversion Following Vernakalant Infusion (Post-Cardiac Surgery Patients)

Table 16.1a.1 Serious Adverse Events (System Organ Class and Preferred Term) by Outcome (Analysis Set) – Investigator Assessment

| | Analysis Set (N=xxx) Outcome | | | | | | | |
|---|---|----------|---|----------|---|----------|---|----------|
| | Recovered | | Recovered with Sequelae | | Not Recovered | | Overall | |
| System Organ Class/ High Level Term/ Preferred Term | Patients n (Cumulative Incidence ¹) | Events n | Patients n (Cumulative Incidence ¹) | Events n | Patients n (Cumulative Incidence ¹) | Events n | Patients n (Cumulative Incidence ¹) | Events n |
| Any SAE | xx (x.x%) | xx |
| SOC 1 | xx (x.x%) | xx |
| HLT 1 | xx (x.x%) | xx |
| PT 1 | xx (x.x%) | xx |
| PT 2 | xx (x.x%) | xx |
| SOC 2 | xx (x.x%) | xx |
| HLT 2 | xx (x.x%) | xx |
| PT 1 | xx (x.x%) | xx |
| PT 2 | xx (x.x%) | xx |

Note: SAE events include reported HOIs that are mapped to specific MedDRA terms.

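### The SmPC effectiveness subgroup (Table 15b) is defined partly by IV antiarrhythmic use up to 4 h after vernakalant, past the 90-minute endpoint, which is expected to raise the on-label conversion rate

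*SAP*

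**What the plan says.** The effectiveness endpoint (Protocol 9.1, SAP 3.3) is the proportion of patients "converted to sinus rhythm for at least one minute within 90 minutes of start of first vernakalant IV administration". SAP 5.10 adds that "a pre-specified secondary analysis of the effectiveness of vernakalant will be restricted to a subgroup of patients who receive vernakalant IV in accordance with the" product label (the SmPC), which it summarises as adult, treated for atrial fibrillation (AF) of permitted duration, and without contraindications.

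SAP 4.3 lists the exclusions that define this subgroup. All but one describe the patient at or before the infusion. The last is "use of class I or class III intravenous anti-arrhythmics within 4 hours before, or within 4 hours after, the start of first vernakalant infusion", which looks both ways from the start of treatment.

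The results go into Table 15b, for which "Template of Table 15a will be applied to the following three tables". That template has three conversion blocks:

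- The first uses the effectiveness population of SAP 4.2, which is everyone "EXCEPT those who receive ECV or IV Class I/III AA for cardioversion within 90 minutes of start of the first vernakalant IV administration".
- The second, by its footnote 3, counts as successes those who "have conversion to sinus rhythm for at least one minute but have no ECV or IV Class I/III AA within overall analysis population" and divides by the full analysis population. Patients given another cardioversion treatment within 90 minutes therefore stay in as non-successes.
- The third (footnote 4) does the same and adds oral propafenone or flecainide to the list.

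**The concern.** The outcome is known 90 minutes after the first infusion starts. Subgroup membership is not known until 240 minutes. Treatment given in between can be a consequence of the outcome: a patient who converted early has little reason to receive another IV rhythm-control drug, while a patient who did not convert may well be given one. Removing such patients from numerator and denominator selects the subgroup partly on the result that it is meant to estimate.

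The filter also disables a safeguard within the SAP. Footnotes 3 and 4 keep patients rescued within 90 minutes in the denominator. In Table 15b those rescued with an IV class I/III drug have already left the subgroup. Those rescued electrically remain and count as non-successes. The rate then depends partly on which rescue was chosen.

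SAP 5.10 calls this analysis pre-specified, and SAP 5.11 sends effectiveness results to CHMP in the interim and final reports. No version of the subgroup restricted to pre-infusion criteria is planned, so a reader could not tell better performance on label from failures removed.

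**Working it through.** The documents give no expected rate, size or precision for Table 15b, so there is no planned figure to reproduce.

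**Timing.** Endpoint window: 90 min. Exclusion window after the start: 4 h = 240 min. Overrun: 240 - 90 = 150 min.

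**Inputs.**
- p: the conversion rate with post-infusion users kept in. Assumed 51.1%, the pooled phase III rate in Protocol Section 3.
- f: the share of otherwise on-label patients given an IV class I/III drug in the 4 h after the start. Not in the documents; assumed.
- q: the share of those users who had not converted by 90 min. Not in the documents; assumed.

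**Formula.** Removing the users takes f(1-q) converters from the numerator and f from the denominator:

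reported rate = (p - f(1-q)) / (1-f).

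This exceeds p if and only if q > 1-p. At p = 0.511 the break-even is q = 48.9%.

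**Reported rate when p = 51.1%.**

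| f | q = 0.6 | q = 0.9 | q = 1.0 |
|---|---|---|---|
| 2% | 51.3% | 51.9% | 52.1% |
| 5% | 51.7% | 53.3% | 53.8% |
| 10% | 52.3% | 55.7% | 56.8% |
| 20% | 53.9% | 61.4% | 63.9% |

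In counts, take 1,000 otherwise on-label patients with 511 converters:
- f = 5%, q = 0.9: 50 leave, 5 of them converters. (511 - 5)/(1,000 - 50) = 506/950 = 53.3%, up 2.2 points.
- f = 10%, q = 0.9: 100 leave, 10 of them converters. 501/900 = 55.7%, up 4.6 points. The exact 95% interval moves from 48.0-54.2% to 52.4-58.9%.

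The direction can reverse. At f = 10% and q = 0.4, (0.511 - 0.06)/0.9 = 50.1%.

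**First block.** SAP 4.2 already removes use for cardioversion within 90 min, so the SmPC filter adds mainly the users from 90 min to 4 h. Suppose 3% are treated within 90 min (all for cardioversion) and 5% between 90 min and 4 h, with q = 0.9 for both:
- SAP 4.2 rule alone: (511 - 3)/(1,000 - 30) = 508/970 = 52.4%.
- With the SmPC filter: (508 - 5)/(970 - 50) = 503/920 = 54.7%, up 2.3 points.

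**Footnote 3 block, same patients, no electrical cardioversion.** With users kept in as the footnote provides, the rate is 508/1,000 = 50.8%. After the SmPC filter it is again 503/920 = 54.7%. I follow the footnote formulas here. The row labels of these blocks read as exclusions, so the shell should state which governs.

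**Direction, from the documents.** Table 12a describes these drugs as given to restore sinus rhythm. Protocol Section 3 gives a median time to conversion of 11-13 minutes among converters in the earlier trials, so most converters would be in sinus rhythm before rescue was considered. Both points suggest a q well above one half. Neither measures it.

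**The case against.** The strongest reply is that the criterion comes from the label. The German annex lists among its contraindications use "within 4 hours prior to, as well as in the first 4 hours after" administration. SAP 5.8 and Table 11 also count post-infusion use as a contraindication, and SAP 5.10 describes a subgroup with none. Protocol Section 3 mentions only "use of intravenous rhythm control antiarrhythmics (class I and class III) within 4 hours prior to vernakalant IV administration", though its list is given by way of example; these passages should be reconciled. The label basis stands as an explanation of why the phrase is there. It does not make an event after the outcome a valid selector for that outcome. Adherence on this point is reported separately in Tables 11 and 12a, so nothing about it is lost.

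A reader might infer that the bias always favours the product. The documents do not support that. The Table 11 flag draws on the Concomitant Medication CRF as well as the Pharmacologic Cardioversion CRF, and Table 12a provides for flutter, ventricular tachycardia, ventricular fibrillation and other rhythms. Use for relapse or a ventricular arrhythmia could remove converters.

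A reader might also infer a large effect by assuming that no converter ever receives such a drug and that many non-converters do. Nothing in the documents supports either assumption. Nor is a test or formal comparison of Table 15b with Table 15a planned.

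Two practical objections also stand. Time to conversion may be missing for retrospective patients (Protocol 7.2.1), as may the vernakalant date or time (Table 12a footnote 2); these patients are 435 of the 810 remaining enrolments in Protocol Appendix I. And at German sites the post-infusion use is an enrolment exclusion. Where that is applied, the patients are absent from Tables 15a and 15b alike.

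**Conclusion.** The point holds as an expected, unquantified upward bias in a secondary subgroup. Table 15b selects patients on treatment that can follow from failure, up to 150 minutes after the endpoint is fixed. The rate rises if more than 1-p of those removed are non-converters, which is likely but not certain. Under the stated assumptions (p = 51.1%, q = 0.9) the increase is 2.2 points at f = 5% and 4.6 points at f = 10%, and 2.3 points in the first-block example. Over f = 2-20% and q = 0.6-1.0 it runs from 0.2 to 12.8 points. The use of 51.1% for the registry, f and q are all assumptions.

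The 4-hours-before half of the criterion is a sound baseline condition. The HOI analyses and Table 15a are not touched. This is a cheap improvement, not a threat to the study's main conclusions.

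**What to change.** In SAP 4.3 and 5.10:

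1. Define the main Table 15b subgroup only by conditions known at the start of the first infusion: age, indication, AF duration, baseline contraindications, and IV class I/III use in the 4 h before.
2. Show the present definition, which also excludes use in the 4 h after, as a labelled sensitivity analysis beside it.
3. In the footnote 3 and 4 blocks, keep patients given an IV class I/III drug within 90 minutes in the denominator as non-successes, as those footnotes already provide.
4. In every block, let patients first given such a drug after 90 minutes keep their recorded 90-minute status.
5. Leave the first block's own 90-minute population rule (SAP 4.2) as it is.
6. Report how many patients have unknown drug or conversion timing. Table 11 classes such drug use as unknown, and the SAP does not say whether those patients stay in the subgroup.
7. Add a note that the German-site enrolment exclusion, where applied, has already removed these patients and that the new definition cannot restore them.

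Cost: edits to two SAP sections and the table shell, one extra version of Table 15b, and no new data. The on-label rate is likely to be slightly less favourable, and the main subgroup will include some patients whom Table 11 flags for post-infusion use, which a footnote should say. The change concerns the analysis only and implies no view on clinical use.

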4.4 Handling Withdrawals and Missing Data

There will be no imputation of missing data. Data will be presented and summarised as it was recorded. Reasonable attempts should be made by the treating physician and/or site personnel to limit the amount of missing data. The proportion of missing data is expected to be low for this study, especially with regard to the details of administration of vernakalant IV and concomitant therapies, collected laboratory values, and occurrence of HOIs during the brief, in-hospital follow-up period. Reasonable attempts will be made to limit the amount of missing medical history and presenting condition data to ensure that important information is captured.

Prospective supplemental data collection of study-specific data elements, such as patient's weight, heart failure NYHA functional class, vernakalant administration and patient monitoring is expected to limit missing data.

4.5 Analysis Software and Coding

SAS® version 9.2 or later will be used for all analyses and data summary tables. All AE and SAE verbatim terms will be coded using MedDRA (version 14.0). Medications will be coded using WHO-DD, Format C (01Mar2011) and the Anatomical Therapeutic Chemical (ATC) Classification System. For the purposes of this study, medications sotalol and sotalol hydrochloride will be re-classified for consistency with the Vaughan Williams Classification of Antiarrhythmic Drugs listed in the Section 5.9 [5]. Thus study programmers will manually reclassify sotalol from the assigned ATC code of C07AA (Beta Blocking Agents, Non-Selective) to the ATC code C01BD (Antiarrhythmics, Class III) in the analysis datasets.

5 STATISTICAL ANALYSIS

Categorical variables (e.g., gender) will be summarised by the number and percentage (%) of patients. For the pre-specified HOIs, both stratified (based on enrolment method, i.e. prospective or retrospective) and unstratified (i.e. overall) cumulative incidences will be reported, and corresponding 95% confidence intervals will be displayed for each such specific HOI. Unless otherwise specified, the 95% confidence intervals around the proportions will be calculated using exact methods described by Clopper and Pearson [3].

Continuous variables (e.g., age) will be summarised using descriptive statistics (number of non-missing values, mean, standard deviation, median, Q1 and Q3, minimum and maximum values).

Some continuous variables will be described using categorizations to provide additional detailed information regarding vernakalant IV administration. For instance, percentage of weight-based dosing recommendation may be described using the following categories: < 70%, 70% to < 85%,

85% to < 95%, 95% to 105%, > 105% to 110%, > 110% and the duration of infusion will be reported in categories such as: < 7 minutes, 7 minutes to < 9 minutes, 9 minutes to 11 minutes, >11 minutes to 13 minutes, > 13 minutes. The categorizations will be based on the empirical data and may be adjusted.

Key results will be presented overall and by patient enrolment method (i.e. prospective or retrospective). Any changes to the analysis over the course of the study will be described in Statistical Analysis Plan (SAP) addendums or amendments. Ad hoc analyses (by country, site, or other) will be performed as requested by the sponsor.

